12.0 Descriptive Factors

- 12.1 ECOG Performance Status: 0 versus 1 versus 2 versus 3.
- 12.2 Sex: Male versus female.
- 12.3 Age: 18-30 versus 31-50 versus 51-70 versus ≥ 70 .
- 12.4 Tumor Size: <5 cm versus 5-10 cm versus 11-15 cm versus >15 cm.

- 12.5 Anatomic location: Proximal upper extremity versus distal upper extremity (including elbow) versus proximal lower extremity (including knee) versus distal lower extremity versus superficial trunk.
- 12.6 Lesion presentation: de novo (biopsy only) versus status post inadvertent excision.
- 12.7 Histology: Undifferentiated pleomorphic sarcoma versus liposarcoma versus leiomyosarcoma versus myxofibrosarcoma versus other histology.
- 12.8 Tumor depth: Superficial and deep to fascia versus deep to fascia versus superficial to fascia.
- 12.9 Radiation Treatment Modality: 3D conformal versus IMRT versus proton therapy.
- 12.10 Neoadjuvant chemotherapy: Yes versus no.
- 12.11 Margin status: R0 vs R1 vs R2.
- 12.12 Surgical closure: Primary closure versus skin graft versus flap.

13.0 Treatment / Follow-up Decision at Evaluation of Patient

As per standard of care, throughout the study, investigators can prescribe any medications/treatments that have been deemed necessary for the well-being and over all treatment of the patient.

- 13.1 A patient is deemed ineligible if after registration, it is determined that at the time of registration, the patient did not satisfy each and every eligibility criteria for study entry. The patient will go off study.
 - If the patient received MR for radiotherapy planning, all data up until the point of confirmation of ineligibility must be submitted.
 - If the patient never received radiation therapy, on-study material must be submitted. No additional follow up is necessary.
- 13.2 Those patients who will not receive any radiation treatment or who will receive radiation treatment elsewhere will go off study.
- 13.3 Inevaluable Patients
If a patient fails to complete radiation therapy for reasons other than toxicity, the patient will be regarded as inevaluable and will be replaced.
- 13.4 Patients with a Major Deviation
A patient is deemed a major violation if:
 - a) PTV_4275 D95% < 90%

AND / OR

b) >25% of PTV_4275 receives $\geq 110\%$ of prescription dose
AND / OR

c) Dose to the organs at risk is more than the recommended limit (Table 2.0)
These patients will be flagged but included in the primary endpoint analysis.
Separate sensitivity analysis will also be performed between the patients with
major violation vs no major violation on major wound complication rate.

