11.0 Treatment Evaluation/Measurement of Effect

- 11.1 Development of a surgical wound complication: Secondary unplanned operation under general or regional anesthesia for wound repair (e.g., debridement, operative drainage, or secondary wound closure including rotationplasty, free flaps or skin grafts); or wound management without secondary operation including invasive procedures (e.g., aspiration of seroma or readmission for wound care such as intravenous antibiotics or persistent deep packing for 120 days or longer).
- 11.2 Local recurrence free survival: Any radiographic or pathologic evidence of recurrent disease inside the CTV and/or beyond the CTV to within a 3 cm distance from the edge of the CTV. Ideally assessed by radiographic imaging in comparison to the treatment fields in order to determine site of recurrence.

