16.3.1 Primary Outcome Analysis

16.3.1.1 Definition: The primary endpoint of this trial is the proportion of patients who experience major wound complications within 120 days of surgical resection of soft tissue sarcoma following preoperative radiation therapy. All patients meeting the eligibility criteria who have signed a consent form and have begun treatment will be evaluable for the major wound complication rate.

16.3.1.2 Estimation: The proportion of major wound complications will be estimated by the number of patients who experience the major wound complications within 120 days following surgery divided by the total number of evaluable patients. 95% confidence intervals using normal approximation to binomial wound complication proportion will be calculated.

16.3.1.3 Over Accrual: If more than the target number of patients are accrued, the additional patients will not be used to evaluate the stopping rule or used in any decision making process; however, they will be included in final endpoint estimates and confidence intervals.

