16.3.2 Secondary Outcome Analysis

16.3.2.1 Local failure is defined any radiographic or pathologic evidence of recurrent disease inside the CTV and/ or to within 3 cm from the edge of the CTV. In the absence of censored patients prior to 5 years, local failure rate at 5 years (LFR5) will be equal to the binomial proportion. LFR5 will be evaluated by the number of patients free of local failure/recurrence at 5 year divided by the total number of evaluable patients. Exact binomial 95%

confidence interval for the point estimate will be provided. In the case of censoring prior to 5 years, LFR5 will be estimated using the Kaplan-Meier method.

- 16.3.2.2 Disease-Free Survival is defined as the time from registration date to the earliest date of documentation of either, local recurrence, regional recurrence, distant recurrence, or death due to any cause, censoring patients who are alive and local recurrence free at the date of last known clinical assessment. The distribution of disease-free survival will be estimated using method of Kaplan-Meier.
- 16.3.2.3 Overall Survival is defined as the time from registration date to death due to any cause, censoring patients alive at the date of last contact. The distribution of overall survival will be estimated using method of Kaplan-Meier.
- 16.3.2.4 Late toxicity is defined as toxicity occurs any time between 3 months and 24 months after completion of hypofractionated preoperative radiation therapy. The rate of \geq grade 2 late toxicities will be estimated by the number of patients with a \geq grade 2 late toxicity divided by the total number of evaluable patients. Exact binomial 95% confidence intervals for the true rate of \geq grade 2 toxicity events will be calculated.
- 16.3.2.5 Pattern of relapse will be evaluated by number of patients with patterns of tumor recurrence such as local recurrence, marginal recurrence, regional recurrence, distant metastasis, and second primary tumor divided by the total number of evaluable patients. Exact binomial 95% confidence interval for the point estimate will be provided.
 - 16.3.2.5.1 Local tumor recurrence is defined as any tumor recurrence inside the CTV.
 - 16.3.2.5.2 Marginal tumor recurrence is defined as any tumor recurrence beyond the CTV to within a 3 cm distance from the edge of the CTV.
 - 16.3.2.5.3 Distant tumor recurrence is defined as any tumor that develops distantly from the primary site of sarcoma.

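### Local failures before surgery can be lost: patients who stop radiation for progression are replaced, and local progression before resection is not an event for local failure or DFS

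*Combined protocol and SAP*

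**What the plan says.** All references are to the combined protocol and SAP.

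- **Who is evaluable.** Section 13.3: "If a patient fails to complete radiation therapy for reasons other than toxicity, the patient will be regarded as inevaluable and will be replaced". Toxicity is the only exception. Sections 16.1.1 and 16.3.1.1 say something different for the wound endpoint: eligible, consented patients who "have begun treatment will be evaluable for the major wound complication rate". Section 16.3.2.6 uses a similar rule for adverse events (eligible and treatment started).
- **Local failure.** Section 11.2 reads: "Any radiographic or pathologic evidence of recurrent disease inside the CTV and/or beyond the CTV to within a 3 cm distance". Section 16.3.2.1 uses the same idea: "Local failure is defined any radiographic or pathologic evidence of recurrent disease inside the CTV", or within 3 cm of its edge. The 5-year figure is calculated as follows: "LFR5 will be evaluated by the number of patients free of local failure/recurrence at 5 year divided by the total number of evaluable patients". If there is censoring before 5 years, Kaplan-Meier is used.
- **DFS.** Section 16.3.2.2: "Disease-Free Survival is defined as the time from registration date". Its events are local, regional or distant recurrence, or death from any cause. Patients who are alive and without local recurrence are censored at their last clinical assessment.
- **Analysis sets.** Relapse patterns (16.3.2.5) are also divided by evaluable patients. No analysis set is named for DFS or OS.
- **After progression.** Footnote 9 to the schedule in section 4.0 is attached to the pre-operative visit as well as the later ones. It moves a patient with any disease progression to yearly survival follow-up, with no further assessments.
- **Residual tumor.** Section 12.11 records it, but only as a descriptive factor: "Margin status: R0 vs R1 vs R2".

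**The concern.** DFS is timed from registration, when most patients still have their tumor, and surgery follows weeks after radiation ends. Two rules can lose local failures in that period.

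First, a patient who stops radiation because the disease progresses is declared inevaluable and replaced. Wherever the denominator is evaluable patients, that is an exclusion that depends on outcome. It also contradicts the sections that keep everyone who started treatment.

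Second, a tumor that grows before resection, or becomes unresectable, has not recurred, because it was never removed. Read literally, the patient has no local-failure event and no local DFS event. Footnote 9 then ends the assessments that might have led to one. The patient can be censored at the moment of failing locally, which is informative censoring.

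What is at stake is how objectives 2.2.1 and 2.2.2 are read. Section 1.0 interprets higher local failure in earlier hypofractionated series as a sign that more dose was needed, and it hypothesizes oncologic outcomes equivalent to historical standards. Early local progression bears directly on that question.

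**Working it through.** **Step 1. The plan's own figure.** Section 16.2 gives 108 evaluable patients for the wound endpoint, from p0 = 0.45, p1 = 0.35, one-sided alpha 0.10 and power 80%. With the one-sample Z-test using S(P0):

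n = [(z(0.90)·√(0.45·0.55) + z(0.80)·√(0.35·0.65)) / 0.10]² = 107.95, rounded up to 108.

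Power at 108 is 80.01%, and 108/0.90 = 120. The figures reproduce and are not in dispute. No sample size or power is given for local failure, DFS or OS.

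**Step 2. Following patients through the text.**

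| Patient | What the rules do |
|---|---|
| Stops radiation for progression | 13.3: inevaluable and replaced. 16.3.1.1: evaluable for the wound endpoint. Local failure and relapse patterns: outside the denominator if 13.3 governs. DFS and OS: not stated. |
| Completes radiation, then progresses locally or becomes unresectable before surgery | Evaluable. No recurrence, so no local event. Footnote 9 ends assessments. DFS event only at death or distant disease; otherwise censored at last assessment. |
| R2 resection without progression | No event at surgery. Footnote 9 is not triggered, so scheduled primary-site imaging continues and a later local failure can be scored. |
| New metastasis before surgery | Can count as distant recurrence (16.3.2.5.3 has no post-surgery limit), so a DFS event. |
| Death | Event for DFS and OS if the patient is kept in the analysis. |

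The gap therefore lies in the first two rows.

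**Step 3. Size of the event-definition gap.** The documents give no rate for these events, so the inputs are assumptions. Take 108 patients with 11 other local recurrences (11/108 = 10.2%, close to the benchmark of 10% or less in section 1.0). Let m patients have an uncounted local failure, and let f be the share of them later scored as recurrences. Censoring is ignored.

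- As written: (11 + f·m)/108
- Counted: (11 + m)/108
- Gap: (1 − f)·m/108

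| m | Counted | Gap, f = 0 | Gap, f = 0.5 |
|---|---|---|---|
| 0 | 11/108 = 10.2% | 0 | 0 |
| 2 | 13/108 = 12.0% | 1.9 points | 0.9 points |
| 4 | 15/108 = 13.9% | 3.7 points | 1.9 points |
| 6 | 17/108 = 15.7% | 5.6 points | 2.8 points |

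At f = 1 the gap is zero. For scale, the exact 95% interval around 11/108 is 5.2% to 17.5%.

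**Step 4. Size of the replacement gap.** Step 3 does not measure the effect of 13.3. If k patients are replaced for progression and then restored as failures, the rate is (11 + k)/(108 + k). For k = 1, 2, 3 this gives 12/109 = 11.0%, 13/110 = 11.8% and 14/111 = 12.6%, against 10.2% without them. These counts are also assumed.

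**The case against.** The strongest reply is that these endpoints are secondary and the objectives are only to report them. No test, margin or decision rule is attached, and the decision rule in 16.2.1 uses wound complications alone. The benchmark in section 1.0 is itself a local recurrence rate, so a definition based on recurrence matches it. Entry requires candidacy for complete macroscopic resection, or a recommended re-resection for negative margins, and radiation lasts three weeks, so progression that stops treatment may be uncommon. All of this stands. It limits the consequence but does not remove the contradiction or the informative censoring.

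Three stronger readings are tempting, and the documents do not support them:

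- **All failures before or at surgery vanish from the oncologic endpoints.** A reader might infer this, but early metastases can count as distant recurrence, and deaths count in DFS and OS. The gap concerns local failures.
- **Replaced patients are dropped from DFS and OS.** Neither definition uses an evaluable denominator. The set is simply not stated, so exclusion is an inference from 13.3.
- **R2 resections are scored as successes.** They are not events at surgery, but these patients stay on scheduled imaging and may be scored later. Whether R2 should count at once as a local failure is debatable against a recurrence-based benchmark.

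It could also be said that recurrence is meant to include progression. The protocol uses progression in footnote 9 and recurrence in the endpoint definitions, so the text does not settle this.

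**Conclusion.** The concern holds for local failures. Section 13.3 conflicts with 16.1.1 and 16.3.1.1, and through the evaluable denominator it can exclude patients from local failure and relapse patterns because of their outcome. Local progression before surgery, including tumor that becomes unresectable, is not an event for local failure or for the local part of DFS. Footnote 9 makes it likely that such a patient is censored as free of local recurrence.

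The size cannot be taken from the documents. With 0 to 6 affected patients among 108, 11 other recurrences, no overlap and no later scoring, 5-year local failure would be 10.2% as written against 10.2% to 15.7% when counted. The gap shrinks if some of these patients are later scored as recurrences, and it is zero if none are affected. The primary endpoint's sample size of 108 does not change. This is worth correcting before analysis, as a matter of secondary, descriptive endpoints.

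**What to change.** 1. Reconcile 13.3 with 16.1.1 and 16.3.1.1. Analyze local failure, relapse patterns, DFS and OS in all eligible patients who began radiation, including any who are replaced. Report how many were replaced and why.
2. In 16.3.2.1 and 16.3.2.2, count documented local progression before surgery, including progression that prevents resection, as a local-failure and DFS event on the date of documentation, instead of censoring at that point. The SAP should say what counts as documentation, because the documents give no progression criterion.
3. As a sensitivity analysis, report local failure and DFS with R2 resection counted as an event at surgery. Also report recurrence after R0/R1 resection, for comparison with historical recurrence rates.

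The cost is mainly protocol and SAP wording; pre-operative imaging of the primary site and margin status are already planned. The reported 5-year local failure and DFS may be slightly less favorable. The main local failure rate would no longer be strictly the same quantity as the historical recurrence rate, which is why the R0/R1 rate is shown beside it.

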7.1.4.4.2 Major Deviation Definition

- a) PTV_4275 D95% $<90\%$
AND / OR
- b) $>25\%$ of PTV_4275 receives $\geq 110\%$ of prescription dose
AND / OR
- c) Dose to the priority 1 organs at risk is more than the recommended limit (Table 2.0)

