7.1.4.5 Organs at Risk Dose Constraints

Normal tissue dose constraints are listed in Table 2.0. Every effort should be made to avoid treating the full circumference of any extremity. There is no special requirement for skin dose limit. However, full prescription dose to skin over areas commonly traumatized (e.g., elbow, knee, shin) should be avoided unless in the PTV.

While every effort should be made to deliver prescription doses to the PTV as specified while adhering to normal tissue constraints, it is recognized that certain anatomical factors may prevent this. As such, if normal tissue constraints are unachievable, the patient will be taken off the trial and treated with standard pre-operative RT to 50 Gy in 25 fractions meeting standardly accepted constraints for that fractionation schedule.

Table 2.0 –Organs at Risk Dose Constraints

Organ at Risk	Dose Constraints	Priority
Bone avoid	Mean < 32 Gy V35Gy < 64% V35Gy < 40%	1 1 2
Soft tissue avoid	Mean < 26 Gy V18Gy < 50%	2 1
Joint (only major joints: hip/knee/shoulder)	V42.56Gy < 50%	2
Anus	Max V42.75Gy (%) V40.6Gy (%)	Report Report Report
Genitalia	Max Mean < 26 Gy	Report 1

Testis (if fertility preservation desired)	V1Gy \leq 60% V1Gy \leq 50%	1 2
Ovaries (if fertility preservation desired)	V4.8Gy \leq 60% V1Gy \leq 50%	1 2
Lungs	V18Gy \leq 20%	1
Brachial plexus	Max $<$ 48 Gy	1
Heart	Mean $<$ 10 Gy	1
Esophagus	Mean $<$ 26 Gy	1
Liver	Mean $<$ 26 Gy	1
Stomach	Max \leq 38 Gy	1
Small Bowel	Max \leq 45 Gy; if in PTV V42.75Gy $<$ 20 cc V26.5Gy $<$ 100 cc V39Gy $<$ 60 cc	21 2 1
Large Bowel	Max $<$ 45 Gy; if in PTV V42.75Gy (%) V40.6Gy (%) V42.75Gy (cc) $<$ 50 cc	2Report Report 2
Kidney	V11.8 Gy $<$ 10% for total kidney volume V11.8Gy $<$ 33% for each kidney V5Gy for each kidney	1 2 Report
Spinal Cord	Max	Report

	V39Gy <0.1%	2
Bladder	Max	Report
	V42.75Gy <50%	2
	V30Gy <60%	2

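### The check on major deviations in section 13.4 compares violators with non-violators, and no test of the primary hypothesis in patients without a major deviation is pre-specified

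*Combined protocol and SAP*

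**What the plan says.** Section 13.4 says of patients with a major deviation: "These patients will be flagged but included in the primary endpoint analysis". The one further analysis is introduced with "Separate sensitivity analysis will also be performed between the patients with", and the comparison is "major violation vs no major violation on major wound complication rate".

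A patient enters the group through any of three criteria: (a) low coverage, "PTV_4275 D95% < 90"%; (b) a large high-dose volume, ">25% of PTV_4275 receives" at least 110% of the prescription; or (c) an organ-at-risk dose over its limit. Criterion (c) is worded in two ways. Section 13.4 has "Dose to the organs at risk is more than the recommended limit (Table 2.0"; section 7.1.4.4.2 has "Dose to the priority 1 organs at risk is more than the recommended limit (Table 2.0".

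The primary hypothesis is set in sections 16.2 and 16.2.1: a one-sample Z-test against 45% at one-sided 10%, in 108 evaluable patients. Section 16.3.1 takes as evaluable all eligible, consented patients who began treatment. Neither section 13.4 nor section 16 defines a set without major deviations, repeats the Z-test in such a set, or reports results by type of deviation.

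**The concern.** A sensitivity analysis should show whether the main conclusion survives a reasonable change in the data set or assumptions. Here the main conclusion is that the complication rate is below 45%. Comparing violators with non-violators asks whether the two groups differ, and a small violator group can seldom answer even that. A non-significant difference could be read as reassurance although the non-inferiority result depends on the violators.

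At stake is the decision in section 16.2.1, that the 15-fraction regimen is not inferior and can go on to larger studies. That claim is about the regimen as specified, and the protocol itself classes these deviations as major.

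**Working it through.** **Inputs from the documents (sections 16.2 and 16.2.4).** Null rate 0.45, assumed true rate 0.35, one-sided alpha 0.10, n = 108, stated power 80.01%, standard error computed at the null rate.

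**1. The plan's own figure.**
n = [(1.2816·√(0.45·0.55) + 0.8416·√(0.35·0.65)) / 0.10]² = 107.95, so 108. Normal-approximation power at 108 is 80.01%. Both reproduce.

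**2. Success boundary.** z = (x/108 − 0.45)/√(0.45·0.55/108).
- 41 events (38.0%): z = −1.470, p = 0.071, success.
- 42 events (38.9%): p = 0.101, failure.

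The exact chance of 41 or fewer events is 8.4% at a true rate of 45% and 77.4% at 35%.

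**3. The contrast can miss a reversal.** Take 41/108 overall, a success. The splits are illustrative.

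| Violators | Non-violators | Z-test against 45% in non-violators | Fisher p, violators vs non-violators |
|---|---|---|---|
| 3/10 | 38/98 (38.8%) | p = 0.108, fails | 0.74 |
| 3/16 | 38/92 (41.3%) | p = 0.238, fails | 0.10 |

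The first row is a near miss at the boundary: the rate moves by less than one point. The second is a clearer change. In neither would the planned contrast reach 5% significance.

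**4. Precision and power of the contrast.** The 95% half-width for the difference, with a common rate of 35% and m violators, is 1.96·√(0.35·0.65·(1/m + 1/(108 − m))):
- m = 5: 43 points
- m = 10: 31 points
- m = 20: 23 points

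If the true rates were 20% in violators and 45% in the rest (assumed), power at two-sided 5% (also assumed, since section 13.4 names no test or level) would be about 33% with 11 violators, 46% with 16 and 58% with 22.

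**5. Effect of inclusion on the primary test.** With k violators at rate v and the other 108 − k truly at 45%,
P(success) = Σₓ P[Bin(k, v) = x] · P[Bin(108 − k, 0.45) ≤ 41 − x].
The values of k and v are assumptions.

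| Violators | Their rate | P(success) |
|---|---|---|
| 10 | 15% | 20.9% |
| 10 | 25% | 15.9% |
| 10 | 45% (no difference) | 8.4% |
| 10 | 55% | 5.8% |
| 10 | 65% | 3.8% |
| 5 | 25% to 35% | 11.7% to 10.0% |
| 3 | 25% to 35% | 10.3% to 9.3% |

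**6. Power of the missing test.** Approximate power at a true 35%, same formula as step 1: 78.6% with 103 patients (about 5% excluded), 76.7% with 97 (about 10%) and 68.8% with 76 (about 30%).

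**The case against.** A reader might infer that the planned analysis cannot show whether under-dosed patients drive a non-inferiority finding, and that keeping violators always pulls the result towards success. The documents do not support either statement.

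- The contrast has to produce the count and rate in non-violators, and testing that rate against 45% is one more line. The information is not lost. What is absent is the commitment to run the test and report it. The half-widths in step 4 describe the group difference, not the precision of the non-violator rate.
- Only criterion (a) is low coverage. Criteria (b) and (c) are excess dose. If those patients have more wound complications, keeping them is conservative, as the 55% and 65% rows show. Excluding all violators would not isolate under-dosing either; that needs results by criterion.
- The usual argument that deviations favour non-inferiority comes from two-arm trials, where they make the arms alike. This is one arm against a fixed 45%, so the direction depends on the type of deviation.
- The 16–21% figures need 10 under-dosed patients with rates of 15–25%. Section 1.0 cites 17% with postoperative radiation, so the low end lies below the rate cited without preoperative treatment. Section 7.1.4.4 requires an explanation when target-dose requirements are missed, and section 7.1.8 requires approval of every plan. Both should keep numbers down. With 3 to 5 such patients at 25–35% the figure is 9.3–11.7%, close to the nominal 10%.

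All four points stand, and they limit the size and direction of the concern. They do not supply a pre-specified check of the primary conclusion. A test chosen after the non-violator rate has been seen carries less weight than one fixed beforehand.

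**Conclusion.** The point holds in limited form. The analysis that section 13.4 presents as a sensitivity analysis is a low-powered group contrast; it does not test whether the non-inferiority conclusion holds in patients treated as planned, and no test of the non-violator rate against 45% is pre-specified. The primary analysis itself is not at fault.

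Neither the direction nor the size of any bias can be fixed from the documents. The range of about 4% to 21% with 10 violators, against 8.4% with no difference, is illustrative and rests on the assumed number of violators, their assumed complication rates and a true 45% in everyone else.

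The violator group is also not uniquely defined, because the two wordings of criterion (c) give different sets. In addition, section 7.1.4.5 says that "if normal tissue constraints are unachievable, the patient will be taken off the trial", whereas section 13.4 keeps patients over the limits in the primary analysis. Both points affect who is counted, and the sections must be reconciled.

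**What to change.** 1. Reconcile criterion (c) between sections 7.1.4.4.2 and 13.4, and both with the off-trial rule in section 7.1.4.5, so that the excluded set is defined before any data are examined.
2. In sections 13.4 and 16.3.1, pre-specify as supportive the one-sided 10% Z-test against 45% in patients without a major deviation, with the estimate and confidence interval, reported beside the primary result. Because the set is smaller, a lost significance should be read together with the shift in the estimate.
3. Tabulate wound complication rates separately for criteria (a), (b) and (c), so that low coverage and excess dose are not averaged together.
4. Label the violator versus non-violator contrast descriptive.

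The cost is one extra analysis and one table on patients who are flagged anyway. The sample size does not change. Power of the supportive test is about 77–79% if 5–10% of patients are excluded, and lower if more are (68.8% at about 30%).
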